## 6.8 Product Receipt and Tracking

Product accountability will not be performed for this study. Devices will be taken from commercial inventory at study sites.

## 6.9 Product Storage

It is the responsibility of the investigator to correctly handle and store market released product. These products will be used according to their labeling.

## 6.10 Product Accountability

Product accountability will not be maintained for this study as the products used are market released in the U.S.

### Product delivery

Commercially available product supply will be managed in a manner consistent with other market-released products.

### Product receipt and tracking

All products used in this study will be market released in the geographies they are used. Device Traceability may be required per local laws and regulations. If there are additional local requirements related to the Ellipsys System beyond what is collected by Medtronic on the eCRF, this is the Investigator's responsibility and should be recorded in the subject's medical records, but will not be collected by Medtronic (e.g., national registration card number, identification code linked to names and contact information, log of all subjects enrolled in the study, lot or batch number).

## 7. Study Site Requirements

---

### 7.1 Investigator/Investigation Site Selection

All investigators managing the subject's endoAVF must be qualified practitioners and experienced in the diagnosis and treatment of subjects with ESRD. All 'Newly Trained Provider' physicians must be trained in the handling of the Ellipsys System.

The role of the principal investigator is to implement and manage the day-to-day conduct of the clinical investigation as well as ensure data integrity and the rights, safety and well-being of the subjects involved in the clinical investigation.

The investigator/investigation site must meet the following minimum criteria:

1. Investigator/site is qualified by training, education, and has relevant experience appropriate to the use of the product and associated procedures.
  - a. Operating physician must be trained in the surgical or percutaneous creation of AV fistulas and/or be trained in minimally invasive percutaneous procedures (e.g., endovascular interventions).
2. Investigator must have experience with medical devices and/or regulated studies.
  - a. Site has participated in at least one pre-market study in the last 5 years.
3. Investigator must have interest in the therapy proposed for this investigation.
4. Investigator/site expects to have adequate staff, time and resources to the conduct the study throughout the duration of the study. Each site must have a designated research coordinator assigned to the study.
5. Investigator/site has access to an adequate number of eligible subjects.
6. Ability to perform duplex ultrasounds.
7. Investigator/site has access to hemodialysis treatment records for enrolled subjects throughout follow-up period according to the study protocol.

***Medtronic Business Restricted***

8. Site has at least one Investigator (Principal or Sub-Investigator) that meets the definition of a Newly Trained User (i.e. has performed  $\leq 10$  Ellipsys cases in a clinical trial or commercial setting OR participated in the Ellipsys IDE Study but performed  $\leq 2$  Ellipsys EndoAVF creation study procedures).
9. Investigator/site has the ability to comply with the protocol, required procedures, applicable Institutional Review Board (IRB) and national/local regulations.
10. Investigator is not debarred, disqualified, or working under sanctions in applicable regions. *U.S. Sites: Investigator has not been excluded from participation in all Federal Health Care programs (e.g. Medicare, Medical, Medicaid). Investigator is not on the list of FDA list of investigators who have been disqualified, restricted, or debarred from conducting clinical studies.*
11. Anticipated study startup timeline, including contracting and IRB and regulatory submission and approval (if applicable) is acceptable.
12. Anticipated competition for same subject population from competitive ongoing studies is at an acceptable rate.

Study site personnel training will be completed and documented prior to participation in this study.

## 7.2 Study Site Activation

During the activation process (prior to subject enrollment), Medtronic will train study site personnel on the clinical investigation plan, informed consent, and on data collection and reporting tools. If new members join the study site team, they will receive training on the applicable study requirements relevant to their role before contributing to the study.

Prior to performing study related activities, all regulatory requirements shall be fulfilled, including, but not limited to the following:

- IRB approval (and voting list, as required by local law) of the current version of the CIP and IC.
- RA approval or notification (as required per local law)
- Fully executed CTA
- Financial disclosure (if applicable)
- CV of investigators and key members of the investigation study site team (as required).
- Documentation of delegated tasks
- Documentation of study training.
- Additional requirements imposed by local regulations, the IRB and RA shall be followed, if appropriate.

In addition, all participating study site staff must be trained on the current version of the CIP as well as on the applicable study requirements depending on their role and must be delegated by the principal investigator to perform study related activities.

Medtronic will provide each study site with documentation of study site/investigator readiness; this letter must be received prior to performing study related activities.

## 7.3 Role of the Sponsor Representatives

Sponsor representatives may provide support at the study site as required for the study under supervision of the Principal Investigator, including:

- Provide study training relevant and pertinent to the involvement of personnel conducting study activities and investigator responsibilities
- Technical support at the EndoAV Fistula Creation Procedure, Week 1, and Week 4 follow-up visits, and as needed during EndoAVF cannulation for hemodialysis under the supervision of a study investigator, but no data entry, shall be performed by Medtronic personnel or their representatives at study sites
- Monitoring and auditing activities
- Duplex ultrasound and vein mapping training visits as well as maturation procedure consultation, as needed

## 8. Selection of Subjects

---

### 8.1 Study Population

This study will be conducted in subjects diagnosed with ESRD or chronic kidney disease on hemodialysis who are medically indicated for the creation of an upper limb anastomosis. Patients who provide informed consent shall be enrolled into this study.

### 8.2 Subject Enrollment

Only subjects who provide written informed consent, meet all inclusion criteria (section 8.3) and none of the exclusion criteria (section 8.4), are considered eligible for enrollment at each study site. When a subject and the principal investigator or authorized designee, as required, have personally signed and dated the IC, the subject is considered enrolled in the study. The date the subject signed the IC must be documented in the subject's medical records.

The decision to use the Ellipsys System will occur at the time of the procedure, based on confirming pre-procedural Inclusion Criteria. The target vessels will be assessed for size and quality (i.e., location, tortuosity, stenosis, degree of calcification) using vascular ultrasound. If a subject's AVF becomes occluded and is abandoned, the subject will not be eligible for re-enrollment into the post market surveillance study. The following criteria will be used to determine the patient's eligibility for enrollment in the study.

### 8.3 Inclusion Criteria

Patients must meet all of the following general inclusion criteria:

1. Male or non-pregnant female  $\geq 18$  years of age and  $\leq 80$  years of age
2. Life expectancy of at least one year, in the investigator's opinion
3. Diagnosed with ESRD or chronic kidney disease on hemodialysis.

***Medtronic Business Restricted***

4. Patients deemed medically eligible for upper extremity autogenous AV fistula creation, per institutional guidelines and/or clinical judgment
5. Adequate quality vein based on pre-operative assessment
  - a. Adjacent vein diameter of  $\geq 2.0$  mm at target anastomosis site
  - b. Confirmed clinically significant outflow
6. Adequate quality radial artery based on pre-operative assessment
  - c. Arterial lumen diameter of  $\geq 2.0$  mm at target anastomosis site
7. Adequate collateral arterial perfusion with patent palmar arch as demonstrated by Barbeau Test or Allen's Test.
8. Radial artery-adjacent vein proximity  $\leq 1.5$  mm measured lumen edge-to-lumen edge as determined by pre-procedural ultrasound and confirmed pre-procedure
9. Patient is able to provide written informed consent and attend follow-up examinations at the enrolling institution

## Imaging-based Inclusion Criteria

The following criteria are to be assessed during the study Index procedure immediately prior to use of the Ellipsys device:

10. Confirm radial artery-adjacent vein proximity  $\leq 1.5$  mm measured lumen edge-to-lumen edge as determined by pre-procedural ultrasound and confirmed pre-procedurally
11. Confirm radial artery and adjacent vein diameter of  $\geq 2.0$  mm at target anastomosis site

## 8.4 Exclusion Criteria

Patients must not meet any of the following general exclusion criteria:

1. Pre-existing ipsilateral vascular disease interfering with the study procedure or potentially confounding the study results including:
  - a. Documented or suspected central venous stenosis ( $\geq 50\%$ ) or
  - b. Upper extremity arterial stenosis or
  - c. Vascular disease at the radial artery / adjacent vein site
2. Prior vascular surgery at or proximal (central) to the AVF target site interfering with AVF maturation or other ipsilateral surgery that could potentially confound the study results such as prior axillary dissection or mastectomy
3. History of steal syndrome from a previous surgical ipsilateral hemodialysis vascular access which required intervention or abandonment
4. Systolic pressures  $< 100$  mm Hg at the time of screening
5. Suspected or confirmed skin disease at the skin entry site
6. Edema of the upper extremity on the ipsilateral side
7. Immunocompromised subjects due to underlying disease or immunosuppressant therapy such as sirolimus (Rapamune®) or Prednisone at a dose of  $> 10$  mg per day

**Medtronic Business Restricted**

[figure not shown]
**CONFIDENTIAL**

056-F275 Rev E Clinical Investigation Plan Template

8. Known bleeding diathesis, coagulation disorder or medications putting the subject at increased risk, in the Investigator's judgment
9. Patients with acute or active infection
10. Scheduled kidney transplant within 6 months of enrollment
11. Participation in another clinical investigation (excluding retrospective studies or studies not requiring a consent form)
12. History of substance abuse or anticipated to be non-compliant with medical care or study requirements based on investigator judgment
13. Patient has an active COVID-19 infection with ongoing sequela or hospitalization for treatment of COVID-19.

## 9. Study Procedures

Refer to Figure 1 for a study flow diagram from patient screening through AVF creation. Subjects enrolled in the study and who undergo a successful AVF creation procedure will be followed for 12 months.

**Figure 1: Flow Diagram from Patient Screening to Subject Follow-Up**

## 9.1 Schedule of Events

The clinical study will require follow-up visits at post-procedure/discharge, 1 week, 4 weeks, 3-, 6-, and 12-months post-index procedure. Table 1 shows a detailed overview of the schedule of clinic evaluations and follow-up visits. Most of the required tests and procedures are considered standard of care for subjects who have a surgical or percutaneous AV fistula created.

**Table 1: Schedule of Assessments and Visit Windows**

Data Collection Requirement / Assessment	Baseline	Index Procedure	Post-Procedure / Discharge	1 Week (± 2 days)	4 Weeks (± 7 days)	3 Months (± 14 days)	6 Months (± 30 days)	12 Months (± 60 days)
Informed Consent	X							
Demographics, Clinical Evaluation, & Vital Signs	X							
Duplex Ultrasound	X 	X 	X	X	X	X	X	X
Study Procedure		X	X					
AVF Evaluation				X	X	X	X	X
Secondary Procedures 		X 	X	X	X	X	X	X
Hemodialysis Records					X 	X 	X 	X 
Subject Satisfaction (VAQ)							X	
Cannulator Satisfaction Survey						X	X	X
Adverse Events and Device Deficiencies 	X	X	X	X	X	X	X	X
Medications	X	X		X	X	X	X	X

The Baseline and Pre-procedure Duplex Ultrasounds are to be performed and assessed by the Investigator/designee only, they will not be submitted to the DUS Core Lab. Beginning with the post-procedure DUS exam through follow-up completion, all DUS images are to be performed according to the Ellipsys PS DUS Protocol and submitted to the DUS Core Lab for analysis.

Additional procedures needed to mature or maintain the AVF or re-establish flow to meet the prescribed dialysis parameters. The need for such procedures will be assessed subsequent to completion of the AVF creation procedure.

Collection through successful 2-needle access of study AVF for >2/3 of sessions over a continuous 28-day period.

Adverse Event and Device Deficiencies assessment is required from the moment the subject is enrolled in the study (i.e. subject signed and dated the informed consent form).

 If an adjunctive procedure is required during the AVF creation procedure, the details of the procedure will be documented on the Adjunctive/Secondary Procedure CRF and will indicate that the adjunctive procedure occurred during the AVF creation procedure.

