#### 3. Functional Cannulation Success Through 12-months:

Defined as the time to achieve successful use of the endovascular AVF, with two-needle access and at least two hours of dialysis through the access, for more than two-thirds of the dialysis sessions over a continuous 28-day period after access creation.

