### Endpoint Definition:

Functional cannulation is defined as the time to achieve successful use of the endovascular AVF, with two-needle access and at least two hours of dialysis through the access, for more than two-thirds of the dialysis sessions over a continuous 28-day period after access creation.

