7.7.7 Ancillary Objective #3

Functional Cannulation Success Through 12-months

Analysis Dataset:

Treated Analysis Set per section **Error! Reference source not found..**

Analysis Method:

Functional cannulation success will be summarized for the Treated population using a Kaplan-Meier curve through at least 12 months. Incidence of success will be characterized as $1-S(t)$ where $S(t)$ is the survival function estimated by the Kaplan-Meier method. Analyses will include probabilities and 95% confidence interval bands through the 12-month visit. The confidence interval will be calculated using a typical transformation of the survival function: $\log(S(t))$. Subjects not completing the study will be censored after their last available visit. For time-to-event analysis, day 0 is date of access creation and final date is day 28 of a 28-day window, in the case of an event, or day of last follow-up.

A sensitivity analysis may be performed where a cumulative incidence curve is estimated and death will be accounted for as a competing risk. The cumulative incidence curve will be descriptively compared to the Kaplan-Meier estimate of incidence.

The observed cumulative incidence estimate may be calculated using the “cmprsk” library in R, with code similar to the following:

```
cmpout1 <- cuminc(time,event)
```

The event variable is 0 if censored, 1 if an event occurs and 2 if a death occurs.

Endpoint Definition:

Functional cannulation is defined as the time to achieve successful use of the endovascular AVF, with two-needle access and at least two hours of dialysis through the access, for more than two-thirds of the dialysis sessions over a continuous 28-day period after access creation.

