Current hemodialysis status for each subject will be summarized 6 and 12 months. The summary will include the number and percentage of subjects on hemodialysis, the most recent access site, Kt/V if the most recent access is the study AVF, and any reasons why the most recent site is not the study AVF. Additionally, the number and percentage of subjects not on hemodialysis will be presented with the reasons.

End of study AVF status will be summarized for the Treated population as the last known AVF status for each subject, including:

- AVF functioning with no intervention
- AVF functioning with intervention, no occlusion
- AVF functioning with intervention, after occlusion
- AVF functioning but not being used
- AVF abandoned prior to initial function
- AVF abandoned after initial function
- Subject not on HD

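### The rule that stops hemodialysis-record collection omits the two-hour element of the functional cannulation endpoint and conflicts with Protocol section 9.10

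*Protocol*

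**What the plan says.** Protocol Table 1 marks Hemodialysis Records at 4 weeks and at 3, 6 and 12 months. Each mark carries footnote 3, which sets the end of collection: "Collection through successful 2-needle access of study AVF for >2/3 of sessions over a continuous 28-day period".

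Protocol section 13.4.3 looks at an unbroken span of 28 days and, within it, defines functional cannulation as use of the fistula "with two-needle access and at least two hours of dialysis through the access, for more than two-thirds of the dialysis sessions". Protocol section 4.1.6 and SAP sections 4.3.1 and 7.7.7 give the same definition. For the Kaplan-Meier analysis, SAP section 7.7.7 sets day 0 at access creation and says that the "final date is day 28 of a 28-day window, in the case of an event, or day of last follow-up".

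Protocol section 9.10 lists Hemodialysis Records among the data required at follow-up visits and gives no stopping point. Two other items on that list, the cannulator survey and the VAQ, do carry explicit visit limits. Protocol section 7.1 makes it a site-selection criterion that the "Investigator/site has access to hemodialysis treatment records for enrolled subjects throughout follow-up period according to the study protocol".

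SAP section 10.2, whose analyses are optional, adds a hemodialysis access summary: "Current hemodialysis status for each subject will be summarized 6 and 12 months". It includes "Kt/V if the most recent access is the study AVF".

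**The concern.** The footnote uses the same two-needle, two-thirds and 28-day terms as the endpoint, so it was evidently written to collect records for as long as the endpoint needs them. It leaves out the two-hour element. A subject whose early two-needle sessions are partly short can therefore satisfy the stopping rule without satisfying the endpoint. If records stop there, the later 28-day period in which the subject does qualify is never recorded.

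What is at stake is the estimate for Ancillary Objective #3. Such a subject would remain in the analysis as someone who never reached functional cannulation. Section 9.10 adds a second problem. A site that follows it keeps collecting, while a site that follows the footnote stops, so how fully the endpoint is captured could differ between sites.

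**Working it through.** **1. The two criteria side by side**

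| Element | Table 1 footnote 3 (stop) | Endpoint (Protocol 4.1.6, 13.4.3; SAP 4.3.1, 7.7.7) |
|---|---|---|
| Two-needle access to the study AVF | required | required |
| Share of sessions | more than 2/3 | more than 2/3 |
| Period | continuous 28 days | continuous 28 days |
| Minimum two hours via the access | not mentioned | required |

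Every window that meets the endpoint meets the footnote, but not the reverse. The stopping rule is strictly looser.

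**2. How small a shortfall separates them**

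The documents give no session frequency. Assume 12 sessions in 28 days. More than 2/3 then means at least 9, since 8/12 = 66.7% is exactly two-thirds. (With 8 sessions the threshold is 6; with 16 it is 11.) A subject with 9 two-needle sessions, 8 of them lasting two hours or more, has 9/12 = 75% for the footnote and 8/12 = 66.7% for the endpoint. The first is met and the second is not: one short session is enough.

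This marginal case is a natural one. If windows are assessed session by session, with 12 sessions in each, the count rises by at most one at a time. A subject coming up from 8 therefore first qualifies at exactly 9.

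**3. Illustration of how often a window would split the two criteria**

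Let k be the number of two-needle sessions among the 12. Assume that each lasts two hours or more independently with probability q. The chance that the footnote is met but the endpoint is not is P(X ≤ 8) with X ~ Binomial(k, q). For k = 9 this is 1 − q⁹; for example, with q = 0.90 it is 1 − 0.387 = 0.61.

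| k | q = 0.80 | q = 0.90 | q = 0.95 | q = 0.98 | q = 1 |
|---|---|---|---|---|---|
| 9 | 0.87 | 0.61 | 0.37 | 0.17 | 0 |
| 10 | 0.62 | 0.26 | 0.09 | 0.02 | 0 |
| 12 | 0.21 | 0.03 | 0.002 | <0.001 | 0 |

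The documents give neither q nor the distribution of k, so these are illustrations and not estimates. They are also not the chance of a missed success: the subject must go on to qualify in a later window that was not recorded.

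**4. Direction of the error**

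Under SAP 7.7.7 a subject without a recorded event runs to last follow-up. A missed success therefore replaces an event at time t₀ with a censored time t₁ at or after t₀. In the Kaplan-Meier product this removes one event at t₀ and keeps one more subject at risk up to t₁. Each factor of S(t) rises or stays the same, so 1 − S(t), the reported success, falls or stays the same at every time.

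**5. Size per subject**

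Ignoring censoring, one missed success lowers the 12-month figure by 1/100 = 1.0 percentage point among the 100 subjects planned to be evaluable, or by 1/134 = 0.75 points among 134. The plan's own sample-size figure reproduces (100/0.75 = 133.3, rounded up to 134) and is not affected by this point.

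**The case against.** The strongest reply is that the footnote abbreviates the endpoint. It speaks of *successful* two-needle access and shares the rest of the endpoint's terms, so the two hours may be implied. That reading is possible, but the text does not state it, and a site completing the Dialysis Treatment Record form works from the footnote. Section 9.10 could also be read as keeping collection open; but it contradicts the footnote and does not say which governs. Records pulled at a visit might reach past the stopping point, though the footnote does not ask for that. It is fair to say that the endpoint is ancillary and descriptive, and that ending session-level collection once the endpoint is truly met is an ordinary way to limit burden.

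Three stronger readings are tempting, and the documents do not support them.

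- *Kt/V is not collected at 6 and 12 months for earlier successes.* This holds only if Kt/V comes solely from the records that the footnote stops. Neither document says so. Protocol Table 2 has a separate Subject Visits form, and SAP section 10.1 places variable locations in an external mapping file. The summary itself is optional.
- *Functional patency is compromised.* That endpoint starts at first two-needle cannulation and ends at abandonment, a clinical determination. AVF evaluation, duplex ultrasound and secondary procedures are collected at visits through month 12, and related and serious adverse events are reported as they occur.
- *Most of the needed session data are lost.* One could count, for success at month 4, the remaining 8 of 12 months as missing. Those sessions are not needed for functional cannulation once it has been achieved.

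**Conclusion.** The concern holds in limited form. The written stopping rule is looser than the endpoint it serves, and it conflicts with section 9.10. Followed as written, it can end collection before a qualifying 28-day period occurs, and the resulting error runs one way, towards understating functional cannulation success.

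The number of subjects affected cannot be derived from the documents. It is zero if every two-needle session lasts at least two hours, or if sites in practice follow section 9.10. The direction rests on the SAP's convention of running non-events to last follow-up. Effects on Kt/V are conditional on a data source that the documents do not name. No primary or secondary endpoint, confidence level or sample-size figure changes.

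**What to change.** Amend footnote 3 of Table 1 so that hemodialysis-record collection continues until the full functional cannulation endpoint is met, including the two-hour element, or through 12 months if it is not met. Amend section 9.10 to state the same rule, so that sites have a single instruction.

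Separately, confirm which form supplies Kt/V for the optional SAP 10.2 summary. If it is only the dialysis treatment record, either provide for it at the 6- and 12-month visits or state that it will be missing for subjects who succeeded earlier.

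The cost is one footnote, one line in section 9.10, and slightly more data entry for the subjects who meet the present stopping rule but not the endpoint. Access to the treatment records throughout follow-up is already a site-selection criterion, so no new source is needed.
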